15.3 Statistical analyses

The primary analysis will take place once the 43rd DFS event has taken place or at the latest after 3 years from the date of surgery of the last included patient.

All efficacy endpoints will be analyzed based on the full analysis population. Supportive analyses based on the PP population will be performed. All safety endpoints will be analyzed based on the safety population. Subgroup analyses for all stratification factors except country are planned for the primary endpoint. All time-to-event endpoints shall have the median value of each treatment group estimated using the Kaplan-Meier method, along with a 95% confidence interval. The number of events of each endpoint shall be presented descriptively by frequency and percentage by treatment arm. The treatment effect will be assessed using Cox regression models with the treatment arm as independent variable and the stratification factors as strata. Cox regression models will also be used to investigate the potential effects of other factors (e.g. chemotherapy given and concomitant therapy) on selected endpoints. Subgroup analyses may be performed for these factors. For the primary analysis, patients who were unblinded before experiencing an event will be censored at the date of the last available tumor assessment before unblinding. A supportive analysis will be performed in which the unblinding will not be considered.

Categorical variables will be summarized with frequency and percentage and may be compared between arms by chi-square tests or Fisher's exact tests. Continuous variables will be summarized using median and range and may be compared between arms by t-tests or Wilcoxon rank sum tests.

Laboratory values will be expressed as the absolute values and as grading according to NCI CTCAE v4.0 by treatment arm. AE grading shall be presented by type, grade, and relation showing frequency and percentage of the within-patient worst grades by treatment arms. In addition, grade ≥ 3 AEs and AEs with relation to treatment ≥ 3 will be summarized separately.

Full analysis details will be outlined in the statistical analysis plan (SAP).

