7.5 Unblinding procedures

Unblinding during the conduct of the trial should be restricted to the cases where there are compelling medical or safety reasons to do so.

If unblinding is considered for non-emergency cases, the local investigator should contact the SAKK CC and the coordinating investigator immediately. Any reasons for unblinding – except for an emergency case – have to be discussed beforehand with the coordinating investigator or the Medical Advisor of the SAKK CC.

For the case that emergency unblinding is necessary:

A scratch off card is provided to the site by the SAKK CC for each patient after the initial DCN allocation (at the start of trial treatment). SAKK CC ensures the correct attribution of a card to each patient by double signatures and documentation.

Sites are responsible to store the card in the investigator's file. In case an investigator breaks the code of a patient, the SAKK CC has to be informed immediately. The investigator will be instructed to keep the information strictly confidential.

Documentation of unblinding:

Any breaking of the code (intentional and unintentional) must be reported and explained via EDC in the CRF "Unblinding" (UB), irrespective of the reason for its occurrence. The unblinding and reason for unblinding must be recorded.

At the time when the trial treatment was prematurely stopped by the sponsor in December 2020 (see section 5), all participating sites received the information about the allocated treatment arm of their

specific patients in order to inform them about the treatment they had received. That allowed the patients to decide together with their treating investigator whether or not to continue aspirin treatment outside of the trial. Since this general unblinding process involved all patients randomized to the trial, with the same date and reason for all of them, it must not be documented on the CRF UB via EDC.

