9 TRIAL TREATMENT

9.1 Treatment overview

Treatment consists of daily intake of 100 mg aspirin (experimental arm) or placebo (control arm) *per os*. Treatment duration is maximum 3 years from treatment start or until tumor recurrence, death, patient refusal or withdrawal by the physician, whichever occurs first. In Q4 2020, the sponsor decided to prematurely stop the accrual of the trial and the trial treatment at the next planned trial visit of each patient. Last patient, last treatment took place in Q2 2021.

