10.2 Reporting of AEs

Patients will be instructed by the investigator to report the occurrence of any AE.

The investigator assesses and records the specified AEs, grade 3 or higher (see section 10.2.1 below), observed during the AE reporting period (from registration until 30 days after the end of trial treatment). Ongoing AEs which are not resolved within 30 days after treatment termination need to be followed-up until resolution or sequelae.

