10.2.1 List of AEs to be reported

The investigator must report AEs, grade ≥ 3 , which are **possibly, probably or definitively related to the trial medication (aspirin/placebo)**. Particular attention should be made to **bleeding-related AEs**, including but not limited to:

- Gastrointestinal hemorrhage with loss of fresh blood per rectum
- Intracranial hemorrhage

AEs associated with concomitant adjuvant chemotherapy must not be reported.

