11.4.2 SAEs after end of trial treatment

During the follow-up phase (starting 30 days after end of trial treatment), the following events have to be reported as SAE:

SAE	Comments
Fatal	Possibly, probably or definitely related to late effects of trial medication.
Life-threatening	Possibly, probably or definitely related to late effects of trial medication.
Disabling	Possibly, probably or definitely related to late effects of trial medication.
Secondary malignancy	Any new malignancy other than a relapse of the current tumor.
Congenital anomaly	Birth defect in neonate/infant or stillbirth.
Other medically significant condition	Possibly, probably or definitely related to late effects of trial medication.

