12.2.1 Year 1 and 2 following surgery

- Assessments to be done at 3*, 6, 9, 12, 15, 18, 21 and 24 months [± 2 weeks]
 - Clinical examination
 - Signs and symptoms of bleeding disorders, including but not limited to: gastrointestinal hemorrhage with loss of fresh blood per rectum, intracranial hemorrhage
 - Laboratory investigations (e.g. hemoglobin, platelets) only if clinically indicated
 - CEA level

In case of significant increase compared to baseline (post-surgery): recurrence must be confirmed by colonoscopy or CT scan or other imaging technique
 - AEs (only while patient is under trial treatment)

Only report AEs grade ≥ 3 potentially related to trial medication
 - Verify patient diary (i.e. patient's compliance to the protocol treatment & patient's intake of acetylsalicylic acid or other NSAIDs or COX-2 inhibitors beside trial treatment)
 - Collect information on concomitant anti-tumor adjuvant chemotherapy (e.g. regimen (doublet or monotherapy) versus no adjuvant chemotherapy, start/end date, etc.)

*) Note: If a patient is included into the trial later than three months after surgery, the visit at 3 months is omitted (and the first trial visit during treatment will take place 6 months after surgery).

- Assessments to be done at 12 and 24 months [± 2 weeks]
 - CT scan chest/abdomen (oral and i.v. contrast strongly recommended)
- Assessments to be done at 12 months [± 2 weeks]
 - Colonoscopy

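### AEs are recorded only if judged related to trial drug, and from December 2020 sites judged this knowing the arm; section 15.3 does not separate those events, leaving the AE comparison open to a modest bias

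*Combined protocol and SAP*

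**What the plan says.** **Entry of events.** Section 10.2: "The investigator assesses and records the specified AEs, grade 3 or higher", from registration to 30 days after treatment ends. Section 10.2.1 limits these to events the investigator considers possibly, probably or definitively related to aspirin/placebo. The visit schedule in 12.2.1 repeats the rule, as does 12.2.2: "Only report AEs grade ≥ 3 potentially related to trial medication". Most SAE categories during treatment carry the same condition (11.4.1). In follow-up, most rows of the table in 11.4.2 read "Possibly, probably or definitely related to late effects of trial medication".

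**Unblinding.** Section 7.5 says that, in December 2020, "all participating sites received the information about the allocated treatment arm of their" patients. It adds that this general unblinding is not to be entered on the unblinding CRF.

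**Dosing after unblinding.** Section 9.1 says the sponsor decided to "prematurely stop the accrual of the trial and the trial treatment at the next planned trial visit of each patient". Sections 5 and 9.1 put last treatment in Q2 2021.

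**Analysis.** Section 15.3: "All safety endpoints will be analyzed based on the safety population". Section 13.1 defines that population as anyone with any dose, with no time limit. Section 15.3 tabulates each patient's worst grade by arm. For the primary analysis it censors patients at the last tumor assessment before unblinding, with a supportive analysis that ignores unblinding. It gives no counterpart for AEs, which are a secondary endpoint (3.2.2).

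**The concern.** A relatedness filter treats the arms alike only while the person applying it does not know the arm. Once the investigator knows a patient is on placebo, a bleed is harder to call drug-related; on known aspirin it is easier. Because the filter decides whether the event is recorded at all, the by-relation breakdown in 15.3 cannot reveal the shift: events judged unrelated or unlikely are generally not collected.

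At stake is the aspirin-placebo contrast in related grade 3 or higher AEs, chiefly bleeding, on which the harm side of the benefit-risk statement rests. As planned, a reader of the AE tables could not tell which attributions were made blinded.

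**Working it through.** The plan gives no figure on this point. The check sets the passages side by side and then sizes the window under stated assumptions.

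**1. Is there an unblinded recording window?** Unblinding is dated December 2020 (7.5). Treatment stops at the next planned visit, the last in Q2 2021 (5, 9.1). AE reporting lasts 30 days more (10.2). Section 7.5 also describes treatment as stopped in December 2020, which does not match. Even on that reading, the 30-day tail and later follow-up SAEs were judged with the arm known.

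**2. Share of AE reporting time affected.** From the documents: 113 randomized (4.1.1), accrual 4.5 years (section 1), treatment at most 3 years, visits every 3 months in years 1-2 and every 6 months in year 3. Assumed: uniform accrual, and 2 to 4 months of reporting after unblinding per patient still on treatment. The average wait to the next visit is 1.5 or 3 months; adding about 1 month gives 2.5 to 4. The extreme is 6 + 1 = 7 months.

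- Still within 3 treatment years: 3/4.5 = 2/3, or about 75 of 113.
- Blinded exposure per patient: (2/3 × 1.5) + (1/3 × 3) = 2.0 years; 113 × 2.0 = 226 patient-years.
- 2 months: 75.3 × 2/12 = 12.6 patient-years; 12.6/(12.6 + 226) = 5.3%.
- 4 months: 25.1 patient-years; 25.1/251.1 = 10.0%.
- 7 months: 43.9 patient-years; 43.9/269.9 = 16.3%.
- If 30% had stopped early (75.3 × 0.7 still on treatment, 226 × 0.85 blinded patient-years), the shares are 4.4%, 8.4% and 13.8%.
- A simulation with 5, 10 or 20% a year stopping gives 16.6, 15.4 or 13.1 unblinded patient-years against 215, 202 or 180 blinded: about 7% each time.

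**3. Effect on a rate ratio.** With unblinded share s, and attribution after unblinding multiplied by a on aspirin and b on placebo, a true ratio of 1.0 becomes (1 − s + s·a)/(1 − s + s·b).

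| s | a = 1, b = 0.5 | a = 1.5, b = 0 |
|---|---|---|
| 5% | 1.03 | 1.08 |
| 10% | 1.05 | 1.17 |
| 16% | 1.09 | 1.29 |

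The multipliers are assumptions; the documents give no evidence on them.

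**4. Effect in percentage points.** Section 2.4 cites gastrointestinal hemorrhage in 2.47% on long-term aspirin and 1.42% on placebo. At 2:1, 113 patients split into about 75 and 38.

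- Expected events: 75 × 0.0247 = 1.85 and 38 × 0.0142 = 0.54, total 2.39.
- Expected in the window: 2.39 × 0.05 = 0.12 to 2.39 × 0.10 = 0.24; at 16%, 0.38.
- Milder scenario (placebo attribution halved): s × 0.5 × 1.42 = 0.04 to 0.07 points for s = 5-10%.
- Stronger scenario (placebo attribution lost, aspirin up 50%): s × (0.5 × 2.47 + 1.42) = s × 2.655, or 0.13 to 0.27 points; at 16%, 0.42.

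The cited rates carry no severity grade, whereas the trial records related events of grade 3 or higher, so these counts may be high.

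**The case against.** The strongest reply is that little depends on this. The AE analysis is mainly descriptive, no decision rule uses it, onset dates are collected (10.2.2) so a split could be made at reporting, and 15.3 defers full details to a SAP. All of that stands, and it limits the weight of the point. But no text supplied provides the split, and the absence of separation is inferred from that silence.

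The contrast with DFS should not be pressed. Section 15.3 gives no reason for censoring at unblinding. Sections 4.1.2 and 7.5 say unblinding let patients decide on aspirin outside the trial, which could affect DFS follow-up far longer than an AE window that closes 30 days after treatment.

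Three stronger inferences are tempting and not supported:

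- *That after unblinding events could enter only from the aspirin arm.* Attribution on placebo may fall, but nothing shows it vanishes. There are also exceptions: 10.2.2 has unscheduled grade 3 or higher laboratory values documented without mentioning relatedness; the secondary malignancy and congenital anomaly rows in 11.4.1 and 11.4.2 state no such condition (though the 11.4.1 lead-in does); and 11.4.1 also admits events related to trial procedures.
- *That every follow-up SAE was judged unblinded.* Inclusion began in Q2 2016, so patients who had completed or stopped treatment before December 2020 were already in follow-up, and their SAEs up to the general unblinding were judged without its influence.
- *That one attribution-driven event, worth 1/75 = 1.3 points, would exceed the 1.05-point excess (2.47 − 1.42).* The arithmetic is right but any single aspirin event does this, blinded or not. At a 7% share only 2.39 × 0.07 = 0.17 bleeds are expected in the window, about a 15% chance of any.

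A cut on onset date alone is also imperfect. With visits 3 to 6 months apart, an event that began in autumn 2020 may first have been judged after unblinding. And removing on-treatment harms from the main safety table would be a debatable trade, so the restricted table should be an addition.

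**Conclusion.** The point holds as a cheap improvement. The AE comparison is open to bias; bias is not demonstrated. The likely direction is more attribution on aspirin and less on placebo. Under uniform accrual and 2 to 4 months of unblinded reporting, about 5-10% of AE reporting time is affected (4-8% if 30% had stopped early; up to 16% at the 7-month extreme). A true rate ratio of 1.0 would then read about 1.03 to 1.17, and a bleeding difference at the cited rates would shift by about 0.04 to 0.27 percentage points. These figures rest on assumed attribution shifts and borrowed rates. With only two or three bleeds expected in total, it is still worth showing which attributions were made with the arm known.

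**What to change.** In section 15.3 or the SAP:

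- Keep the all-event AE tables on the safety population.
- Add a by-arm AE/SAE table limited to events before the earlier of the patient's own unblinding and the December 2020 general unblinding. Apply the limit to onset and, where its date is available, to the causality assessment. If only onset is available, say so in a footnote.
- List later events by arm, marked as judged unblinded.
- Take the general unblinding date from sponsor notification records, because 7.5 keeps it off the unblinding CRF.
- State as a limitation that events judged unrelated were generally not recorded and cannot be recovered by analysis.
- Reconcile section 7.5 (treatment stopped in December 2020) with sections 5 and 9.1 (next planned visit, last treatment Q2 2021), since the length of the unblinded window depends on it.

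The cost is wording, a date reconciliation, one table and one listing. No new patient data are needed and the efficacy analysis is unchanged. The restricted table loses roughly 5-10% of AE exposure, but the full table remains beside it.

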- Presence of predefined, activating PIK3CA mutation in exons 9 or 20
- Complete curative tumor resection (R0) within 14 weeks maximum before registration
- Adequate performance status (PS 0-2) and hematological values
- No multiple adenocarcinomas of the colon
- No rectal cancer
- No severe or uncontrolled cardiovascular disease
- No upper gastrointestinal bleeding within 12 months prior to registration; no bleeding disorder that is an absolute contraindication to the use of aspirin
- No regular intake of acetylsalicylic acid or other non-steroidal anti-inflammatory drugs (NSAIDs) or cyclooxygenase (COX)-2 inhibitors
- No systemic rheumatic diseases or degenerative disorders affecting the musculoskeletal system with a relevant risk of requiring treatment with NSAIDs in the future
- No concurrent treatment with other experimental drugs, no administration of concomitant drugs contraindicated for use with the trial drug (the concomitant use of adjuvant chemotherapy for

stage III and high risk stage II colon cancer according to international treatment guidelines is allowed)

TRIAL DURATION

Duration of accrual: Initially planned 3 years, actual duration until premature closure of the trial (see section 5) 4.5 years

Duration of trial therapy (per patient): maximum 3 years (or until recurrence, death or consent withdrawal)

Duration of the follow-up (per patient): at least 3 years (from the date of surgery)

Duration of trial (in total): 7.5 years

The trial may be stopped early based on the results of two interim efficacy analyses or if new scientific data become available which change assessment of risk/benefit.

TRIAL SCHEDULE

Trial activation: Q2 2016

First patient in: Q2 2016

Last patient in: Q2 2019 (initially planned); Q4 2020 (after premature closure)

Last patient last treatment: Q2 2022 (initially planned); Q2 2021 (after premature closure)

Last patient last visit: Q2 2029 (initially planned); Q4 2023 (planned after premature closure)

TRIAL PRODUCT

Aspirin® (acetylsalicylic acid) is a salicylate drug that has analgesic, anti-inflammatory, antipyretic and antiplatelet properties. Aspirin is part of a group of medications called non-steroidal anti-inflammatory drugs, but differs from most other NSAIDs in the mechanism of action.

The comparator used in this trial is placebo, and both, aspirin or placebo are taken orally once daily.

TRIAL TREATMENT

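### Primary DFS is censored at unblinding and all patients were unblinded in December 2020, yet the primary analysis is still timed and powered on 43 DFS events; section 15.3 does not say how the two fit together

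*Combined protocol and SAP*

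**What the plan says.** - **Censoring (15.3).** The rule for primary DFS is that "patients who were unblinded before experiencing an event will be censored at the date of the last available tumor assessment before unblinding". No kind of unblinding is excepted. The next sentence adds: "A supportive analysis will be performed in which the unblinding will not be considered".
- **General unblinding (7.5, also 4.1.2).** When "trial treatment was prematurely stopped by the sponsor in December 2020 (see section 5), all participating sites received the information" on the arm of each of their patients, so that patients could be told. The reason given for not recording it case by case is: "Since this general unblinding process involved all patients randomized to the trial, with the same date and reason for all of them". It is therefore not to be entered on the unblinding CRF, whereas any individual code break must be.
- **Timing (15.3).** "The primary analysis will take place once the 43rd DFS event has taken place or at the latest after 3 years" from the last included patient's surgery.
- **Design figures (15.1).** 43 events and 80% power, with 185 patients planned. Section 4.1.1 reports 113 randomized.
- **Follow-up (5, 12.3).** Foreign sites stopped in Q2 2021. Swiss sites continue until their last patient reaches 3 years from surgery.
- **Model (15.3).** "The treatment effect will be assessed using Cox regression models with the treatment arm as independent variable and the stratification factors as strata". Remaining details are left to an SAP that is not part of the supplied text.

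**The concern.** Put 15.3 and 7.5 together and the primary DFS data are frozen in December 2020: every patient still event-free on that date is censored at an assessment before it. The trigger keeps running into 2023, on events that the analysis leaves out. Section 15.3 does not say whether those events count toward 43.

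Two things are at stake. First, the 43 events and 80% power in 15.1 do not describe the information that the literal primary analysis will hold. Second, two analysts could build two different primary data sets from the same text, one censoring everyone at the general unblinding and one censoring only individual code breaks. If that is settled only at analysis, it is settled after allocations were released to sites.

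**Working it through.** **1. The plan's own figure.** The hazard ratio is ln(0.85)/ln(0.70) = 0.456. With events split about evenly between arms under the alternative (information 1/4 per event), a fixed one-sided 5% test with 80% power needs (1.645 + 0.842)² / (0.25 × 0.785²) = 40.1 events. A simulated inflation factor of 1.067, for O'Brien-Fleming-type benefit and non-binding futility looks at 25% and 50%, gives 42.8, so 43. The same boundaries give critical hazard ratios of 0.10 and 0.34 at 11 and 22 events (protocol: 0.11 and 0.34). The 43 is sound as a design figure.

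**2. Calendar limit.** The last patient entered in Q4 2020 (section 1), at most 14 weeks after resection (6.1.6). The last surgery therefore lies between 25 June 2020 (1 October minus 14 weeks) and 31 December 2020, and the 3-year limit between 25 June and 31 December 2023. That is about 2.5 to 3 years after unblinding.

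**3. Events under the literal rule.**
- From the documents: 113 patients at 2:1; accrual over 4.5 years; hazards −ln(0.70)/3 = 0.1189 and −ln(0.85)/3 = 0.0542 per year.
- Assumed: uniform entry; unblinding 4.6 years after the first entry; loss of 0 or 20% by 3 years (loss hazard μ = 0 or 0.0744).

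Expected events per arm, with θ = λ + μ, are n(λ/θ)[1 − (e^(−0.1θ) − e^(−4.6θ))/(4.5θ)]. Without loss:
- placebo: 37.67 × [1 − (0.9882 − 0.5787)/0.5350] = 8.8
- aspirin: 75.33 × [1 − (0.9946 − 0.7794)/0.2438] = 8.8

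The total is 17.7, or 15.9 with 20% loss. Counting the up to 14 weeks from surgery to entry as time at risk raises the upper end to about 19.

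**4. Power.** Φ(√(D·i) × 0.785 − 1.645), with i = 2/9 or 1/4:
- D = 15.9, i = 2/9: Φ(1.880 × 0.785 − 1.645) = 43%
- D = 17.7, i = 1/4: Φ(2.104 × 0.785 − 1.645) = 50%

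This is unstratified. Simulated power for the literal rule is 42 to 49% with 8 strata (stage, side, exon), and 34 to 43% with 24 (three countries assumed).

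**5. Sensitivity and comparison.**

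| Scenario | Expected events | Formula power at HR 0.456 |
|---|---|---|
| Literal rule, HR 0.456, uniform accrual | 16–18 | 43–50% |
| Literal rule, HR 0.456, early- to late-heavy accrual | 11–23 | 35–59% |
| Literal rule, no effect, uniform accrual | 24–27 | – |
| Literal rule, no effect, early- to late-heavy accrual | 17–34 | – |
| Unblinding ignored, HR 0.456, uniform accrual, Swiss share 30–80% | 22–33 | 53–73% |

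The last row follows Swiss patients to 7.5–7.6 years and foreign patients to 5.0–5.1 years after the first entry. It ignores any dilution after treatment stopped. The Swiss share is not in the documents.

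**6. Can 43 be reached?** Binomial(113, D/113):
- Literal rule, HR 0.456: at most about 1 in 100,000, even with early-heavy accrual.
- Unblinding ignored, HR 0.456, uniform accrual: at most about 3% at an 80% Swiss share and 11% at 100%.
- Unblinding ignored, HR 0.456, early-heavy accrual without loss: about 15% and 32%.
- Unblinding ignored, no effect, uniform accrual, Swiss share 30–80%: about 2 to 85%.

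**The case against.** The best counter-argument is that the rule was never meant for the general unblinding. Individual code breaks must be entered on the unblinding CRF and the general one must not, so the unblinded patients in 15.3 may be those with such a record. This is plausible, and every literal-rule figure above depends on rejecting it. But 15.3 does not refer to the CRF or limit the rule, so the text leaves the matter open.

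Second, the plan can be carried out. The calendar limit gives a date on either reading, and one date for all endpoints is a reasonable choice. Later Swiss follow-up still feeds the supportive DFS analysis and possibly TTR, OS and CSS, for which the rule's scope is not stated. This stands: the wait adds nothing to literal primary DFS, but it does not bias it. A reader might infer that the primary analysis cannot be done. The documents do not support that.

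Third, a reader might infer that 43 events are out of reach on any reading. Step 6 shows otherwise: if all follow-up events count, early-heavy accrual or absence of effect could bring the event limb into play.

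Fourth, 15.1 is the original design calculation, and the protocol openly reports the closure. This is fair, but 15.3 still uses 43 as a live trigger. Finally, the SAP may settle all of this, so the recommendation is conditional on it.

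**Conclusion.** The point holds as an unresolved inconsistency in the primary analysis and should be fixed. As worded, 15.3 and 7.5 together exclude all DFS events after December 2020, while the trigger, the 43 events and the 80% power are unchanged. Under the literal rule about 16 to 18 events and 43 to 50% unstratified power are expected at HR 0.456 with uniform accrual. Across accrual shapes this is 11 to 23 events and 35 to 59%; with no effect it is about 17 to 34 events. These are model-based figures; the actual count is not in the documents.

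It would be wrong to infer that the censoring rule alone costs the trial its 43 events. The literal shortfall is 25 to 27 events (43 − 17.7; 43 − 15.9). With unblinding ignored, 17 to 21 would still be missing at a 30% Swiss share and 10 to 15 at 80%. Closure at 113 patients and the end of foreign follow-up are thus the main cause over most of the assumed range. The exception is a high Swiss share with little loss, where the rule weighs at least as much. Confidence is medium, because the narrower reading is credible and the SAP was not available.

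**What to change.** Unless the SAP already does so, and before comparative DFS data are viewed:

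1. State in 15.3 whether the general unblinding triggers the censoring rule. If it is exempt, record this as a decision made after allocations were released to sites.
2. Make the event count, the trigger and the data cut-off refer to the events that the primary analysis uses. If the rule stands, the primary DFS cut-off is the unblinding date, and the 43-event or 3-year trigger applies only to the supportive and other analyses.
3. Keep the version not chosen as the supportive analysis, and say whether the rule extends to TTR, OS and CSS.
4. Label 43 events and 80% power as the original design figures, and give the expected events and power of the closed trial under stated assumptions.

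Two side points can be reconciled in the same edit: the exact unblinding date (7.5 gives only the month), and the end of Swiss follow-up (Q4 2023 in section 5, Q3 2024 in 12.3).

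The cost is a few sentences in 15.1, 15.3 and the SAP. Both analyses are already foreseen and no new data are needed. Keeping the rule means accepting the smaller event count. Exempting the general unblinding means declaring a late decision and accepting possible dilution from stopped treatment or open-label aspirin.
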